# 9.2.1 Patient Evaluation After Permanent Discontinuation of Protocol Therapy, Post-Unblinding

Sites should complete the evaluations for the current reporting period as per section 9.2. Subsequently, evaluations can switch as follows:

Investigations		Timing from Randomization		
Physical Examination	
 
Physical examination
 
Vital signs
 
Weight + ECOG Performance status
 
	Every 4 weeks (every 28 days) after randomization until the first regularly scheduled 4 week assessment at which the patient has been off study therapy for a minimum of 28 days.		
Adverse Events 	
 
Adverse Event evaluation must be done at each study visit for the preceding reporting period
 
Report ongoing AEs thought to be related to BBI608
 
	Every 4 weeks (every 28 days) after randomization until the first regularly scheduled 4 week assessment at which the patient has been off study		
Overall Survival	Assess for survival of patient 	therapy for a minimum of 28 days, and every 8 weeks (56 days) thereafter.		
Other Anti-cancer Therapy				
Other	• Serum or urine pregnancy test 	Every 4 weeks (every 28 days) after randomization		
Investigations	Serum CEA			
Hematology	CBC + differential, Platelet count			
Biochemistry	Creatinine, Total Bilirubin, ALT,     Alkaline Phosphatase, LDH, Albumin,     Potassium, Magnesium, Phosphate	until the first regularly scheduled 4 week assessment at which the patient has been off study therapy for a minimum of 28 days		
Urinalysis	Dipstick (including protein, specific gravity, glucose and blood)			
Cardiology Assessment	• ECG	At the first regularly scheduled 4 week assessment at which the patient has been off study therapy for a minimum of 28 days		
Radiology & Imaging (only if done)	CT/MRI scan as per baseline assessment with tumour measurement and evaluation by RECIST 1.1 criteria 	No longer required every 8 weeks after randomization until objective disease progression. However if radiology and imaging is done, please report the data in EDC on the disease assessment (target and non-target lesion) tables. 		
Correlative Studies & Tissue Banking	• Submission of whole blood sample to central tumour bank 	At 4, 8 and 12 weeks after randomization 		

Adverse events will be recorded and graded according to the NCI Common Terminology Criteria for Adverse Events (see Appendix V).

 In the event that patient is unable to attend clinic, post-progression follow-up may be by means of telephone contact.

 In women of childbearing potential only. The minimum sensitivity of the pregnancy test must be 25 IU/L or equivalent units of HCG.

 The same method of assessment and the same technique should be used to identify and report each lesion at baseline and at reassessment during treatment. Tumour evaluations will continue until progressive disease is documented (as described in section 10).

 Details for collection, processing, storing and shipping these samples will be provided in a separate procedure manual.

#### 10.0 CRITERIA FOR MEASUREMENT OF STUDY ENDPOINTS

#### 10.1 Definitions

- 10.1.1 Evaluable for Adverse Events: All patients who have received at least one dose of BBI608/placebo will be evaluable for adverse events from the time of their first dose of BBI608/placebo.
- 10.1.2 Evaluable for Overall Survival (OS): All randomized patients will be included in the analysis of OS, which is defined as the time interval between the date of randomization and the date of death from any cause. Patients who are still alive at the time of the final analysis, or who have become lost to follow-up will be censored at their last date known to be alive.
- 10.1.3 Evaluable for Progression Free Survival (PFS): All randomized patients will be included in the analysis of PFS, which is defined as the time interval between the date of randomization and the date of objective disease progression or death, whichever comes first. If neither event has been observed, then the patient will be censored at the date of the last tumour assessment.

Disease progression is defined as objective progression per RECIST 1.1 [Eisenhauer 2009]. It is required to perform, whenever possible, a radiological confirmation of the clinical suspicion of tumour progression. In the situation where there is clinical suspicion of progression but objective progression cannot be determined per RECIST 1.1, disease is defined as clinical deterioration without objective evidence of progression.

An observed increase in tumour marker (e.g. CEA), regardless of the magnitude of increase, will **NOT** be considered evidence of objective disease progression.

The date of disease progression is defined as the date when the criteria for objective progression are first met.

- 10.1.4 Evaluable for Disease Control Rate (DCR): All patients who have been randomized will be included in the analysis of DCR which is defined as a composite of Stable Disease, Partial Response and Complete Response as classified according to the definitions set out below [Eisenhauer 2009]. For patients who discontinue protocol therapy prior to their first objective assessment of response, it is imperative that an objective response assessment be undertaken as close to the protocol specified schedule as possible in order to ensure patient data contributes appropriately to the interim assessment of DCR (see section 14.5).
- 10.1.5 Evaluable for Quality of Life Assessment: All patients who have completed the baseline quality of life questionnaire and at least one other QoL questionnaire are evaluable.
- 10.1.6 Evaluable for Health Utilities: All patients who have completed the baseline health utilities assessment questionnaire and at least one other health utilities assessment questionnaire are evaluable.

# 10.2 Response and Evaluation Endpoints

Response and progression will be evaluated in this study using the revised international criteria (1.1) proposed by the RECIST (Response Evaluation Criteria in Solid Tumours) committee.

10.2.1 Measurable Disease: Measurable *tumour lesions* are defined as those that can be accurately measured in at least one dimension (longest diameter to be recorded) as ≥ 20 mm with chest x-ray and as ≥ 10 mm with CT scan, or clinical examination. Bone lesions are considered measurable only if assessed by CT scan and have an identifiable soft tissue component that meets these requirements (soft tissue component ≥ 10 mm by CT scan). *Malignant lymph nodes* must be ≥ 15mm in the short axis to be considered measurable; only the short axis will be measured and followed. All tumour measurements must be recorded in millimetres (or decimal fractions of centimetres). Previously irradiated lesions are not considered measurable unless progression has been documented in the lesion.

- 10.2.2 Non-measurable Disease: All other lesions (or sites of disease), including small lesions are considered non-measurable disease. Bone lesions without a measurable soft tissue component, leptomeningeal disease, ascites, pleural/pericardial effusions, lymphangitis cutis/pulmonis, inflammatory breast disease, lymphangitic involvement of lung or skin and abdominal masses followed by clinical examination are all non-measurable. Lesions in previously irradiated areas are non-measurable, unless progression has been demonstrated.
- 10.2.3 Target Lesions: When more than one measurable tumour lesion is present at baseline all lesions up to a maximum of 5 lesions total (and a maximum of 2 lesions per organ) representative of all involved organs should be identified as target lesions and will be recorded and measured at baseline. Target lesions should be selected on the basis of their size (lesions with the longest diameter), be representative of all involved organs, but in addition should be those that lend themselves to reproducible repeated measurements. Note that pathological nodes must meet the criterion of a short axis of ≥ 15 mm by CT scan and only the short axis of these nodes will contribute to the baseline sum. All other pathological nodes (those with short axis ≥ 10 mm but < 15 mm) should be considered non-target lesions. Nodes that have a short axis < 10 mm are considered non-pathological and should not be recorded or followed (see 10.2.4). At baseline, the sum of the target lesions (longest diameter of tumour lesions plus short axis of lymph nodes: overall maximum of 5) is to be recorded.

After baseline, a value should be provided on the CRF for all identified target lesions for each assessment, even if very small. If extremely small and faint lesions cannot be accurately measured but are deemed to be present, a default value of 5 mm may be used. If lesions are too small to measure and indeed are believed to be absent, a default value of 0 mm may be used.

- 10.2.4 Non-target Lesions: All non-measurable lesions (or sites of disease) plus any measurable lesions over and above those listed as target lesions are considered *non-target lesions*. Measurements are not required but these lesions should be noted at baseline and should be followed as "present" or "absent".
- 10.2.5 Response: All patients will have their BEST RESPONSE from the start of study treatment until the end of treatment classified as outlined below:

Complete Response (CR): disappearance of *target* and *non-target*. Pathological lymph nodes must have short axis measures < 10 mm (Note: continue to record the measurement even if < 10 mm and considered CR). Residual lesions (other than nodes < 10 mm) thought to be non-malignant should be further investigated (by cytology specialized imaging or other techniques as appropriate for individual cases [Eisenhauer 2009]) before CR can be accepted.

Partial Response (PR): at least a 30% decrease in the sum of measures (longest diameter for tumour lesions and short axis measure for nodes) of target lesions, taking as reference the baseline sum of diameters. Non target lesions must be non-PD.

Stable Disease (SD): neither sufficient shrinkage to qualify for PR, nor sufficient increase to qualify for PD taking as reference the smallest sum of diameters on study.

Progressive Disease (PD): at least a 20% increase in the sum of diameters of measured lesions taking as references the smallest sum of diameters recorded on study (including baseline) AND an absolute increase of  $\geq$  5mm. Appearance of new lesions will also constitute progressive disease (including lesions in previously unassessed areas). In exceptional circumstances, unequivocal progression of non-target disease may be accepted as evidence of disease progression, where the overall tumour burden has increased sufficiently to merit discontinuation of treatment or where the tumour burden appears to have increased by at least 73% in volume. Modest increases in the size of one or more non-target lesions are NOT considered unequivocal progression. If the evidence of PD is equivocal (target or non-target), treatment may continue until the next assessment, but if confirmed, the earlier date must be used.

Table 1: Integration of Target, non-Target and New Lesions into Response Assessment:

Target Lesions	Non-Target Lesions	New Lesions	Overall Response	Best Response for this Category also Requires		
Target lesions ± non target lesions						
CR	CR	No	CR	tumour nodes < 10mm		
CR	Non-CR/Non-PD	No	PR			
CR	Not all evaluated	No	PR			
PR	Non-PD/ not all evaluated	No	PR			
SD	Non-PD/ not all evaluated	No	SD	documented at least once ≥ 5 wks. from baseline		
Not all evaluated	Non-PD	No	NE			
PD	Any	Any	PD			
Any	PD	Any	PD			
Any	Any	Yes	PD			
Non target lesions ONLY						
No Target	CR	No	CR	tumour nodes < 10mm		
No Target	Non-CR/non-PD	No	Non-CR/non-PD			
No Target	Not all evaluated	No	NE			
No Target	Unequivocal PD	Any	PD			
No Target	Any	Yes	PD			

Note: Patients with a global deterioration of health status requiring discontinuation of treatment without radiological progression having been observed at that time should be reported as "symptomatic deterioration". This is NOT objective PD. Every effort should be made to document the objective progression even after discontinuation of treatment.

# 10.3 Response Duration

Response duration will be measured from the time measurement criteria for CR/PR (whichever is first recorded) are first met until the first date that recurrent or progressive disease is objectively documented, taking as reference the smallest measurements recorded on study (including baseline).

#### 10.4 Stable Disease Duration

Stable disease duration will be measured from the time of randomization until the criteria for progression are met, taking as reference the smallest sum on study (including baseline).

# 10.5 Methods of Measurement

The same method of assessment and the same technique should be used to characterize each identified and reported lesion at baseline and during follow-up. Assessments should be identified on a calendar schedule and should not be affected by delays in therapy. While on study, all lesions recorded at baseline should have their actual measurements recorded at each subsequent evaluation, even when very small (e.g. 2 mm). If it is the opinion of the radiologist that the lesion has likely disappeared, the measurement should be recorded as 0 mm. If the lesion is believed to be present and is faintly seen but too small to measure, a default value of 5 mm should be assigned. For lesions which fragment/split add together the longest diameters of the fragmented portions; for lesions which coalesce, measure the maximal longest diameter for the "merged lesion".

- 10.5.1 Clinical Lesions. Clinical lesions will only be considered measurable when they are superficial and  $\geq 10$  mm as assessed using callipers (e.g. skin nodules). For the case of skin lesions, documentation by colour photography including a ruler to estimate the size of the lesion is recommended. If feasible, imaging is preferred.
- 10.5.2 Chest X-ray. Chest CT is preferred over chest X-ray, particularly when progression is an important endpoint, since CT is more sensitive than X-ray, particularly in identifying new lesions. However, lesions ≥ 20 mm on chest X-ray may be considered measurable if they are clearly defined and surrounded by aerated lung.
- 10.5.3 CT, MRI. CT is the best currently available and reproducible method to measure lesions selected for response assessment. This guideline has defined measurability of lesions on CT scan based on the assumption that CT slice thickness is 5 mm or less. When CT scans have slice thickness greater than 5 mm, the minimum size for a measurable lesion should be twice the slice thickness. MRI is also acceptable in certain situations (e.g. for body scans). Other specialized imaging or other techniques may also be appropriate for individual case [Eisenhauer 2009]. For example, while PET scans are not considered adequate to measure lesions, PET-CT scans may be used providing that the measures are obtained from the CT scan and the CT scan is of identical diagnostic quality to a diagnostic CT (with IV and oral contrast).
- 10.5.4 Ultrasound. Ultrasound is not useful in assessment of lesion size and should not be used as a method of measurement. If new lesions are identified by ultrasound in the course of the study, confirmation by CT is advised.
- 10.5.5 Endoscopy, Laparoscopy. The utilization of these techniques for objective tumour evaluation is not advised. However, they can be useful to confirm complete pathological response when biopsies are obtained or to determine relapse in trials where recurrence following complete response or surgical resection is an endpoint.
- 10.5.6 Cytology, Histology. These techniques can be used to differentiate between PR and CR in rare cases (for example, residual lesions in tumour types such as germ cell tumours, where known residual benign tumours can remain).

The cytological confirmation of the neoplastic origin of any effusion that appears or worsens during treatment when the measurable tumour has met criteria for response or stable disease is mandatory to differentiate between response or stable disease (an effusion may be a side effect of the treatment) and progressive disease.

#### 11.0 SERIOUS ADVERSE EVENT REPORTING

The descriptions and grading scales found in the NCI Common Terminology Criteria for Adverse Events (CTCAE) will be utilized for Adverse Event (AE) reporting (version can be found in Appendix V). All appropriate treatment areas should have access to a copy of the CTCAE. A copy of the CTCAE can be downloaded from the CTEP web site: (http://ctep.cancer.gov/protocolDevelopment/electronic\_applications/ctc.htm).

All serious adverse events (SAE) defined as per ICH guidelines (see below) and other adverse events must be recorded on case report forms. In addition, all "reportable" serious adverse events are subject to expedited reporting using the NCIC CTG SAE form. The term 'reportable SAE' is used in the definitions which follow to describe those SAE's which are subject to expedited reporting to NCIC CTG.

## 11.1 Definition of a Protocol Reportable Serious Adverse Event

- All serious adverse events must be reported in an expedited manner (see section 11.2 for reporting instructions). These include events occurring during the treatment period (until 30 days after last protocol treatment administration).
- A serious adverse event (SAE) is any adverse event that at any dose:
  - results in death;
  - is life-threatening;
  - requires inpatient hospitalization or prolongation of existing hospitalization (excluding hospital admissions for study drug administration, transfusional support, scheduled elective surgery and admissions for palliative or terminal care);
  - results in persistent or significant disability or incapacity;
  - is a congenital anomaly/birth defect.
- NOTE: Serious adverse events which are unequivocally related to the underlying malignancy or disease progression do NOT require expedited reporting. These include such adverse events as admission for pain control, palliative care or paracentesis of malignant effusions.
- In addition, the following events will **NOT** be recorded as AEs (or SAEs):
  - lack of efficacy /disease progression (will be recorded separately on CRF);
  - laboratory abnormalities for protocol specified tests (these are derived electronically from actual values supplied and need not be reported separately in adverse event tables on CRFs);
  - elective hospitalization for medical, radiological or surgical procedures for treatment of disease or to simplify treatment for study procedures (will be recorded separately on CRF):
  - hospitalization for palliative care or pain control.

Medical and scientific judgement should be exercised in deciding whether expedited reporting is appropriate in other situations such as important medical events that may not be immediately life-threatening or result in death or hospitalization and which are NOT definitively related to the underlying malignancy or disease progression but may jeopardize the patient or may require intervention to prevent one of the events listed above.

AMEND #3: 2014-OCT-01

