# 8.1.4 Dose Modification

The major adverse events associated with the use of BBI608 are gastrointestinal issues (nausea, diarrhea, and abdominal cramping) and fatigue. Fatigue is often secondary to gastrointestinal events. There is no hematologic toxicity associated with BBI608.

The guidelines that follow outline dosing modifications and recommended interventions should the above adverse events occur.

Adverse events will be graded using the NCI Common Terminology Criteria for Adverse Events (CTCAE) (see Appendix V). If a patient experiences several adverse events and there are conflicting recommendations, please use the recommended dose adjustment that reduces the dose to the lowest level.

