#### 8.1.5 Hematologic Adverse Events

No hematologic toxicity related to BBI608 treatment has been observed. Should a study subject experience a Grade 1 or 2 hematologic adverse event, dosing may continue while an alternate explanation is sought and/or a therapeutic intervention is undertaken.

In the unlikely event of a Grade 3 or 4 hematologic adverse event, continued dosing will be at the discretion of the study investigator. Since a Grade 3 or 4 hematologic event attributed to BBI608 has not been reported, a prompt evaluation for an alternate explanation is strongly recommended.

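### Section 11.1 contradicts itself on pain-control admissions, and gives no SAE route for a laboratory abnormality that is itself serious

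*Protocol*

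**What the plan says.** Section 11.0 requires SAEs and other adverse events to be entered on case report forms. Section 11.1 opens with "All serious adverse events must be reported in an expedited manner" and defines seriousness, including inpatient hospitalization. That criterion has its own exclusions. They name palliative or terminal care but not pain control.

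A NOTE follows: "Serious adverse events which are unequivocally related to the underlying malignancy or disease progression do" not have to be expedited. Admission for pain control is one of its examples.

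A further list then names events that will not "be recorded as AEs (or SAEs". Two of its items matter here:

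- "laboratory abnormalities for protocol specified tests (these are derived electronically from actual values supplied"), so that no separate entry in the AE tables is needed.
- "hospitalization for palliative care or pain control", with nothing further.

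Section 8.1.4 gives the major BBI608 adverse events as "gastrointestinal issues (nausea, diarrhea, and abdominal cramping) and fatigue".

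**The concern.** The same admission is treated in different ways within one section, and the most restrictive rule is the one with no causal condition. Because abdominal cramping is a known effect of the drug, an admission to control pain is not always a cancer event. A site that follows the last item would file no SAE for a drug-related admission; a site that follows the NOTE would file one. SAE counts would then depend on which line was read.

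The laboratory item raises a smaller form of the same problem. It is there to avoid double entry, but it also switches off SAE recording, because the list header names SAEs expressly. Section 11.1.1 (related SAEs after unblinding) and section 11.4 (serious, unexpected and related events forwarded to regulators) both need an event that has been classed as serious and judged for relatedness.

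**Working it through.** The plan gives no figure to reproduce, so the check sets the provisions side by side.

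**Pain-control admission, four provisions**

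| Provision (section 11.1) | Condition on cause | Effect |
|---|---|---|
| First bullet | none | all SAEs expedited |
| Hospitalization criterion | none; pain control not among its exclusions | a pain-control admission is serious |
| NOTE | unequivocally due to malignancy or progression | not expedited, but still an adverse event |
| Last list item | none | recorded neither as AE nor as SAE |

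For an admission caused by BBI608, the first three rows make it an expedited SAE and the fourth removes it. The rows cannot all be followed.

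**Alternative route for each listed item**

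1. Lack of efficacy or progression: recorded separately on the CRF.
2. Protocol-specified laboratory abnormalities: derived from the submitted values.
3. Elective hospitalization: recorded separately on the CRF.
4. Palliative-care or pain-control hospitalization: none stated.

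Three of the four items name another place where the information goes; the pain-control item does not.

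**Overlap with the drug's profile.** Section 8.1.4 names abdominal cramping as a major toxicity. The supportive-treatment table in section 8.1.6 includes systemic opioids for diarrhea and cramps. An admission for severe cramping could therefore reasonably be described as one for pain control.

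**What is lost.** The item removes the hospitalization, not the symptom. Cramping remains a gradable AE, and remains an SAE if it meets another criterion such as being life-threatening. The loss is confined to events whose only seriousness criterion is the admission.

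**Laboratory item.** Section 9.1 specifies CBC with differential, platelets, nine chemistry analytes and dipstick urinalysis every 4 weeks. The values arrive, so abnormalities can be graded. The section states no relatedness assessment and no expedited route for them. On timing:

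- SAE route (section 11.2): preliminary report within 24 hours.
- Routine route (Appendix IV): Treatment Report due within 2 weeks of the end of a 4-week period, so up to 4 + 2 = 6 weeks after a value seen at the start of the period.

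Section 8.1.5 shows that the protocol itself regards such findings as attributable: "Since a Grade 3 or 4 hematologic event attributed to BBI608 has not been reported". Section 11.1 removes the AE entry in which the attribution would be made.

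**The case against.** The strongest reply is that little is actually lost. Laboratory data are collected on schedule, and the item is a sensible rule against entering them twice. The illness behind a value (bleeding, infection, arrhythmia, diarrhea) is not on the list and stays reportable. The pain-control item follows a NOTE about malignancy-related events, so cancer pain is a natural reading. Section 11.1 closes with a paragraph allowing medical judgement on expediting, and the electronic data capture guidebook, which is not at hand, may collect attribution on the laboratory forms.

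Most of this stands, and it rules out stronger conclusions that a reader might draw:

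- That serious toxicity of these kinds is never attributed or reported. Values are captured, and symptoms and diagnoses remain recordable.
- That the statement in section 8.1.5 about hematologic events cannot be tested in this trial. The trial is randomized and placebo-controlled, so laboratory grades can be compared between arms without investigator attribution.
- That a given number of events is missing, or more on BBI608 than on placebo. The protocol gives no rate from which either could be derived.

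The reply does not remove the conflict. The natural reading is not the written one: the list is introduced as an addition to the NOTE and drops its condition. The judgement paragraph is discretionary, addresses expedited reporting in situations other than those already described, and does not say that it overrides the list.

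**Conclusion.** The point holds as an inconsistency in safety reporting. The pain-control item is the main defect: it contradicts the NOTE and the general SAE rule, and on its literal wording a BBI608-related admission for cramping loses its SAE status and expedited report. The laboratory item is secondary: an abnormality that itself meets an SAE criterion has no stated 24-hour report or relatedness assessment.

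The size cannot be expressed as a count of events. Its extent is bounded: for pain, events serious only because of the admission; for laboratory tests, events in which the abnormal value is itself the event. The conclusion assumes that sites apply the list as written and that no guidebook instruction corrects it. It still matters after unblinding, because some patients may continue BBI608 and section 11.1.1 requires their related SAEs to be expedited. With accrual closed at 282 patients, a correction acts mainly on those still receiving the drug.

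**What to change.** Two wording changes in section 11.1, sent to sites with a short memo:

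1. Last item: *hospitalization for palliative care, or for pain control unequivocally related to the underlying malignancy or disease progression*. This brings in the NOTE's causal condition.
2. Add to the laboratory item: *except that a laboratory abnormality meeting an SAE criterion and not unequivocally due to the malignancy is reported as an SAE with attribution*.

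There is no need to require an AE entry for every laboratory change that leads to a dose change or treatment; that would be a data-collection preference and would resolve no contradiction. The changes affect reporting only, not treatment. The cost is an amendment and a few additional SAE forms.
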